9.1 Adverse Events

An AE is defined as any untoward medical occurrence, including those AEs that result from dosing errors, which may present during administration of a study drug or during a reasonable follow-up period and which does not necessarily have a causal relationship with the study drug(s). All AEs reported or observed from the first dose of study drug in Period 1 through the Day 36 End of Study Visit will be recorded on the AE page in the eCRF.

All AEs will be followed until the AE is resolved or stabilized as determined by the investigator and/or the medical monitor. Subjects will be instructed to contact the investigator at any time after randomization if any symptoms develop.

A serious AE (SAE) is defined as any AE that results in any of the following outcomes: death, a life-threatening AE, inpatient hospitalization or prolongation of existing hospitalization, a congenital anomaly or birth defect, a persistent or significant incapacity or substantial disruption of the ability to conduct normal activities of daily living. Important medical events that may not result in death, be life threatening, or require hospitalization may be considered serious when, based upon appropriate medical judgment, they may jeopardize the subject and may require

medical or surgical intervention to prevent one of the outcomes listed in this definition. All SAEs reported or observed from the first dose of study drug in Period 1 through follow-up telephone call on Day 59 (+4 days) will be recorded on the AE page in the eCRF.

In addition, the investigator (or designee) must report any Grade 3 (severe) AE that they deem possibly, probably, or definitely related to study drug to the medical monitor and SIGA within 24 hours after becoming aware of the event.

The AE's relationship to study treatment will be evaluated by the investigator. The following relationships will be collected on eCRF: definitely related, probably related, possibly related, unlikely related, or not related.

The AEs that are evaluated as definitely, probably, or possibly related will be considered treatment-related AEs for summary purpose.

The severity of AEs will be classified by the investigator as mild, moderate, severe, life threatening, or death.

An overall AE summary will be generated presenting the frequency and percentage of subjects and the number of AEs for the following:

- Any AE
- Any treatment-related AE
- Any moderate AE
- Any treatment-related moderate AE
- Any treatment-related severe AE
- Any SAE
- Any treatment-related SAE
- Any AE leading to early discontinuation
- Any death

All AEs will be coded using MedDRA (version to be delineated in the CSR). The AEs will also be summarized by system organ class (SOC), preferred term (PT), by severity and relationship to study treatment.

The AE summary tables will be sorted by SOC and PT. System organ class will be displayed in descending order of overall frequency then alphabetically. Preferred term will be displayed in descending order of overall frequency and then alphabetically within SOC. A subject with 2 or more events within the same level of summarization will be counted only once in that level using the most severe incident or most related incident. Percentages will be based on the number of subjects in the safety population.

In summaries of AEs by treatment, AEs will be summarized according to the most recent treatment received prior to the AE onset. For example, an AE that occurred on or after

administration of the study drug on Day 1 of Period 1 but before the administration of study drug on Day 1 of Period 2 will be summarized for study drug administered in Period 1. All AEs will be presented in a data listing. Separate data listings will be generated for treatment-related AEs, SAEs, and AEs leading to study discontinuation.

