5.3 METHOD OF ASSIGNING SUBJECTS TO TREATMENT GROUPS

Randomization will occur according to the randomization schedule before study drug administration on Day 1 of Period 1 after it has been confirmed that the subject fulfills all eligibility criteria. Subjects will be randomly assigned to receive study drug in 1 of 4 treatment sequences (ABCDE, ACEBD, ADBEC, and AEDCB) in 1:1:1:1 ratio.

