6.2 SAFETY ASSESSMENTS AND ENDPOINTS

Safety and tolerability will be assessed by monitoring and recording of AEs, clinical laboratory test results (hematology, serum chemistry, pregnancy, and urinalysis), vital sign measurements (systolic and diastolic blood pressures, heart rate, respiratory rate, and body temperature), 12-lead ECG results, and physical examination findings. Adverse events will

be assessed from the time of the first dose of study drug in Period 1 until the follow-up telephone call on Day 59 (+4 days).

For all safety assessments, the investigator will determine whether results are clinically significant or not clinically significant. Clinical significance is defined as any variation in a result that has medical relevance and may result in an alteration in medical care (eg, active observation, diagnostic measures, or therapeutic measures). If a clinical significance change from baseline is noted, the result and reason for significance will be documented and an AE reported on the AE page in the subject's eCRF. The investigator will continue to monitor the subject until the result has reached the reference range or the result at screening, or until the investigator determines that follow-up is no longer medically necessary.

When procedures are overlapping and occurring at the same time point, the order of procedures should be ECG, vital sign measurements, and then blood collection, with the blood collection scheduled to occur at the nominal time point, unless dictated by other study events happening at that time, such as dosing requirements.

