General study descriptors, as in subject disposition, demographics, protocol deviations, and enrollment characteristics, will be summarized for all randomized subjects, regardless of treatment sequence. Otherwise, safety outcomes, as in adverse events, lab values, vital signs, and electrocardiogram measures, will be summarized by treatment. The treatments below will be used for such presentation:

- TPOXX
- TPOXX + Sevelamer Carbonate
- TPOXX + Sucroferric Oxyhydroxide
- TPOXX + Calcium Acetate
- TPOXX + Lanthanum Carbonate

All data listings will be sorted by treatment and subject number.

No algorithm for imputation of missing data will be employed. Missing data will be treated as missing. If partial data exists for concomitant medications, the start dates will be imputed to the first of the month (for missing day) or first of the year (for missing day and month) for purposes of assigning a prior mediation flag.

There are no plans to derive visit windows; visits will be used in the analyses as reported on the eCRF.

Study days are calculated with respect to the first dose date as below:

- If the assessment/observation date is on or after the first dose date, then Study Day = Assessment/Observation Date First Dose Date + 1;
- Otherwise, Study Day = Assessment/Observation Date First Dose Date

Baseline will be defined as the day the subject checks in (Day -1) before the first dose of study drug administration, unless otherwise specified.

For summary of safety assessments, if there are repeated measurements at a time point, the first non-missing assessment at that time point will be used in the summary tables.

Unscheduled results will not be included in the summary tables, except for determining Baseline, but will be presented in data listings.

The methodology and data handling specifications for PK data are detailed in Section 8.

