4.1. Sample Size

The sample size (N = 44 [to allow at least 36 enrolled subjects to complete]) for this study is based on clinical and practical considerations and not on a formal statistical power calculation. The sample size is considered sufficient for the objectives of the study.

Prior estimates of within-subject variability (CVw) of a single dose of 600 mg TPOXX were obtained from Study SIGA-246-018, which evaluated the single-dose PK of TPOXX in a similar population. The CVw% for Cmax, AUC_{0-24} and AUC_{0-inf} ranged from 11.39% to 12.62%, 9.38% to 18.12%, and 15.70% to 18.02%, respectively.

For a sensitivity analysis, a range for CVw of 10%, 15%, and 20% across point estimates of 0.9, 1.0, and 1.1 will be explored. For the sensitivity analysis, assuming a range of CVw, a sample size of 36 evaluable subjects, it is estimated that the precision (ie, half-width of the 90% confidence interval [CI] on the log and ratio scale), and CI with tolerance probability of 80% on

the original scale for each point estimate will be:

				90%
	Half-Width	Half-Width		Confidence
CVw (%)	(log scale)	(original scale)	Point Estimate	Interval
10	0.043	0.044	0.9	(0.862, 0.94)
			1.0	(0.958, 1.044)
			1.1	(1.054, 1.148)
15	0.065	0.067	0.9	(0.843, 0.96)
			1.0	(0.937, 1.067)
			1.1	(1.031, 1.174)
20	0.086	0.090	0.9	(0.826, 0.981)
			1.0	(0.918, 1.09)
l			1.1	(1.009, 1.199)

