4.3. Analysis Population

The analysis populations are as follows:

- The PK Population will include subjects who receive at least 1 dose of TPOXX and have sufficient concentration data to support accurate estimation of at least 1 PK parameter.
- The Safety Population will include all subjects who receive any amount of study drug.

5. Subject Disposition

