8.4 Pharmacokinetic Statistical Analysis

A linear mixed model with sequence, treatment, and period as fixed effects and subject within sequence as a random effect will be performed on the natural log-transformed values of AUCs (AUC $_{0-24}$, AUC $_{0-48}$, AUC $_{0-t}$, and AUC $_{0-inf}$) and C $_{max}$ to assess the effect of phosphate binders on the PK of TPOXX. The geometric least square means and corresponding 90% CIs will be computed for AUCs and C $_{max}$ of TPOXX + phosphate binder versus TPOXX alone by taking the anti-log of the least squares means from the linear mixed-effect model on the natural logarithms of the corresponding PK parameters. A 90% CI for the ratio will be constructed as the anti-log of the confidence limits of the mean difference. No adjustment will be made for multiplicity.

It will be concluded that there is no relevant interaction of phosphate binders on TPOXX if the 90% CIs for AUCs and C_{max} ratios (TPOXX + phosphate binder/TPOXX alone) are completely contained within the (80%, 125%) interval.

Non-parametric methods will be used to examine median differences in T_{max} for TPOXX.

The geometric mean ratios and corresponding 90% CIs for AUCs and C_{max} for TPOXX will be presented in forest plots for overall assessment of the DDI.

9. Safety Analysis

All safety summaries and analyses will be based upon the safety population.

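### SAP 9.1 divides by-treatment adverse event counts by the whole safety population, so, read literally, dropout or missed binder doses lower the printed binder percentages but not the TPOXX-alone percentage

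*Combined protocol and SAP*

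**What the plan says.** - **Denominator.** SAP 9.1: "Percentages will be based on the number of subjects in the safety population".
- **Population.** SAP 4.3: "The Safety Population will include all subjects who receive any amount of study drug". The definition has no per-treatment part.
- **Layout.** SAP 4 (General Statistical Considerations): "safety outcomes, as in adverse events, lab values, vital signs, and electrocardiogram measures, will be summarized by treatment". It then names five treatments, TPOXX alone and TPOXX with each of the four binders.
- **Numerator.** SAP 9.1, in the paragraph after the denominator rule: "AEs will be summarized according to the most recent treatment received prior to the AE onset".
- **Analysis set.** The opening of SAP 9: "All safety summaries and analyses will be based upon the safety population".
- **Sequences.** Protocol 5.3 randomizes subjects to "1 of 4 treatment sequences (ABCDE, ACEBD, ADBEC, and AEDCB) in 1:1:1:1 ratio". A is TPOXX alone and always falls in Period 1.
- **Size.** SAP 4.1: "The sample size (N = 44 [to allow at least 36 enrolled subjects to complete".

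Protocol 7.3.2 asks for adverse events by treatment and overall but gives no denominator. The SAP's table index labels the adverse event tables only with the safety population. No section makes the number dosed with a treatment the denominator for that treatment's column.

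**The concern.** The numerator belongs to one treatment and the stated denominator does not. In a crossover, a subject who withdraws after Period 2 cannot have an event on a treatment scheduled for Periods 3 to 5, but the literal rule keeps that subject in the denominator for each of those treatments. A missed binder dose has the same effect.

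The error runs one way. TPOXX alone is always given first, so everyone in the safety population has received it and its percentage is correct. Binders are given only in Periods 2 to 5, so only their percentages can fall. The secondary objective is the safety and tolerability of TPOXX with the binders. In a side-by-side reading of the columns, the binder treatments would look somewhat better tolerated than TPOXX alone for a reason unrelated to tolerability.

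**Working it through.** **The plan's own figures.** The plan states no adverse event percentage or denominator count, so there is none to reproduce. Its relevant figures are 44 enrolled and at least 36 completing, an allowance of 44 − 36 = 8 losses (8/44 = 18.2%).

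**Inputs**
- Safety population: 44 (SAP 4.1), taking all enrolled subjects as dosed in Period 1, with no replacement.
- Sequences ABCDE, ACEBD, ADBEC and AEDCB (protocol 5.3). By period the treatments are: Period 1 A, A, A, A; Period 2 B, C, D, E; Period 3 C, E, B, D; Period 4 D, B, E, C; Period 5 E, D, C, B. Each binder therefore occurs once in each of Periods 2 to 5.
- Timing of losses: not in the documents, so three patterns are shown.
- True event rate: not in the documents. 20% on every treatment is assumed, with 10% and 30% as a range.

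**Formulas**
- Mean number dosed per binder = (sum of the numbers dosed in Periods 2 to 5) / 4.
- Printed percentage under the literal rule = true rate × number dosed / 44.
- The share of the true percentage that is printed is therefore number dosed / 44.

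| Pattern of the 8 losses | Dosed, Periods 1–5 | Mean dosed per binder | Share | True 20% prints as |
|---|---|---|---|---|
| No losses | 44, 44, 44, 44, 44 | 44 | 44/44 = 1.00 | 20.0% |
| All after Period 4 | 44, 44, 44, 44, 36 | (44+44+44+36)/4 = 42 | 42/44 = 0.95 | 19.1% |
| 2 before each of Periods 2–5 | 44, 42, 40, 38, 36 | (42+40+38+36)/4 = 39 | 39/44 = 0.89 | 17.7% |
| All before Period 2 | 44, 36, 36, 36, 36 | 36 | 36/44 = 0.82 | 16.4% |

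TPOXX alone is 44/44 = 1.00 in every row and prints 20.0%. Across the three loss patterns, a true 10% prints as 8.2% to 9.5% for a binder, and a true 30% as 24.5% to 28.6%.

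**Single binders.** The table averages over binders; one binder can differ. Suppose losses are even and the 2 losses before each of Periods 3, 4 and 5 all come from ABCDE. Then B is dosed in 42, C in 40, D in 38 and E in 36. These span the possible range for one binder, 36/44 = 0.82 to 42/44 = 0.95. If each loss is equally likely to come from any sequence (an assumption), each extreme has probability (1/4)² × (1/2)² × (3/4)² = 0.0088. About 98% of outcomes therefore lie between 37/44 = 0.84 and 41/44 = 0.93.

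**Replacement.** Protocol 4.4.4 permits it. If all 8 leave before Period 2 and 4 or 8 replacements complete, the share is (36+4)/(44+4) = 40/48 = 0.83 or (36+8)/(44+8) = 44/52 = 0.85. Replacement softens the effect but does not remove it.

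**After the fix.** Take 9 subjects with an event on a binder that 36 received. The literal rule prints 9/44 = 20.5%; dividing by the number dosed gives 9/36 = 25.0%. The TPOXX-alone percentage is the same under both rules.

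**The case against.** The strongest reply is that the sentence only names the analysis set. It closes a paragraph about sort order and counting each subject once, and the rules for by-treatment summaries begin in the next paragraph. A programmer could well put the number dosed at the head of each column. This reading is possible. But SAP 9 had already named the analysis set, the sentence in 9.1 says what percentages are based on, and the SAP holds an index of tables without shells. The documents neither confirm nor exclude column Ns.

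The second reply is that little depends on these percentages, and this stands. No test, threshold or conclusion uses them. The halting rules in protocol 4.4.3 work on numbers of subjects. SAP 9.1 prints counts beside percentages, and correct percentages can be recomputed from the study drug administration listing.

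Third, the 8 losses are a sizing allowance, not a forecast. Subjects stay in the clinic from Day −1 to Day 31, and no dropout rate is stated. This also stands: the result is a range that starts at no effect.

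A reader might go further and infer that the tables will certainly be wrong, or that a binder safety signal would be hidden. The documents do not support either. The wording is open to a harmless reading, the relative reduction at 36 completers averages at most 18% over binders, and the counts stay visible.

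**Conclusion.** The point holds as a defect in a stated rule. Followed as written, it understates binder percentages relative to TPOXX alone once any subject leaves before a binder or misses its dose. At the plan's allowance of 8 losses without replacement, the average binder share is 0.95 with late losses, 0.89 with even losses and 0.82 with losses before Period 2. The share falls below this range only if completion falls below plan. The printed percentages also rest on the assumed 20% rate; the shares do not. The sentence should be corrected, but the effect is modest and descriptive.

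A reader might infer that the interaction conclusion is affected. It is not: it rests on the PK population and a mixed model that use no adverse event percentage.

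A reader might also attach the adverse event end date to this point. That is a separate, minor item. Protocol 6.2 has adverse events "be assessed from the time of the first dose of study drug in Period 1 until the follow-up telephone call on Day 59" (+4 days), and 6.2.1.2 and 6.2.1.3 agree, whereas SAP 9.1 stops non-serious events at the Day 36 visit; these need reconciling. It would be too strong to say that early withdrawers are left without provision, because the relevant schedule column in both documents covers the end-of-study visit or early termination.

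**What to change.** In SAP 9.1, replace the denominator sentence with: *By-treatment percentages are based on the number of safety-population subjects who received that treatment; overall percentages are based on the safety population.* Show these Ns as column headers in the adverse event tables.

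The cost is one sentence in a SAP still marked as a draft, plus column Ns in the table shells. It needs no new data, no extra analysis and, for this point, no protocol change.

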1.4 POTENTIAL RISKS AND BENEFITS

1.4.1 Potential Risks

The effect of TPOXX on a fetus or nursing baby is not yet known; therefore, women of childbearing potential participating in this study will be required to agree to use an acceptable means of birth control from signing of the informed consent form (ICF) and continuing through 30 days after the last dose of study drug. Pregnancy testing will be performed at the screening visit and checked by the investigator for negative pregnancy on Day –1 of each period before administration of study drug. Women who are pregnant or lactating or plan to become pregnant within 3 months after study drug administration will be excluded from the study; if a female subject becomes pregnant during study participation, study drug dosing will be discontinued, and the subject will be withdrawn from the study (Section 6.2.1.8).

As with all drugs, there is potential risk of an allergic reaction. At this time, there is no definitive information on the allergic activity of TPOXX. Headache and nausea have been the most common adverse events (AEs) in clinical studies completed to date. There may be other side effects of TPOXX that are not yet known. Full details can be found in the TPOXX full prescribing information.³

A single dose of the phosphate binders should not lead to any major AEs, but there may be an increased risk of hypercalcemia (specifically with calcium acetate). Other potential AEs include diarrhea, dyspepsia, nausea, vomiting, abdominal pain, flatulence, and hypotension (specifically with sucroferric oxyhydroxide).

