6.2.1.1 Adverse Event Definitions

An AE is defined as any untoward medical occurrence, including those AEs that result from dosing errors, which may present during administration of a study drug or during a reasonable follow-up period and which does not necessarily have a causal relationship with the study drug(s). An AE is any unfavorable and unintended sign (eg, a clinically significant abnormal laboratory finding), symptom, or disease temporally associated with the use of a medicinal product, whether or not considered to be related to the medicinal product. All AEs will be followed until the AE is resolved or stabilized as determined by the investigator and/or the medical monitor. Subjects will be instructed to contact the investigator at any time after randomization if any symptoms develop.

A treatment-emergent AE is defined as any event not present before exposure to study drug or any event already present that worsens in intensity or frequency after exposure to the study drug.

An adverse reaction is any AE caused by a study drug. Adverse reactions belong to a subset of all suspected adverse reactions and indicate that there are reasons to conclude that the study drug caused the event.

A suspected adverse reaction is any AE for which there is a reasonable possibility that the study drug caused the AE. For the purposes of investigational new drug safety reporting, "reasonable possibility" means that there is evidence to suggest a causal relationship between the study drug and the AE. A suspected adverse reaction implies a lesser degree of certainty about causality than an adverse reaction, which means any AE caused by a study drug.

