6.2.1.5 Assessment of Severity

All AEs will be graded for intensity according to the current DAIDS Table for Grading the Severity of Adult and Pediatric Adverse Events Version 2.1 July 2017.⁵

Any laboratory or clinical AE that is not listed on the DAIDS Table will be assessed for severity and classified into 1 of 5 clearly defined categories as follows:

- Grade 1 (Mild): Events require minimal or no treatment and do not interfere with the subject's daily activities.
- Grade 2 (Moderate): Events result in a low level of inconvenience or concern with the therapeutic measures and may cause some interference with normal functioning.
- Grade 3 (Severe): Events interrupt a subject's usual daily activity, may require systemic drug therapy or other treatment, and are usually incapacitating.
- Grade 4 (Life-threatening): Event that, in the opinion of the investigator, places the subject at immediate risk of death from the reaction as it occurred (ie, it does not include a reaction that, had it occurred in a more severe form, might have caused death).
- Grade 5 (Death).

Changes in the severity of an AE should be documented to allow an assessment of the duration of the event at each level of intensity to be performed. An AE characterized as intermittent requires documentation of the onset and duration of each episode.

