7.3.2 Safety Analyses

Adverse events will be coded by preferred term and system organ class using the latest version of the Medical Dictionary for Regulatory Activities and summarized by treatment and overall. All AE data will be presented in a data listing. Treatment-emergent AEs will be summarized by treatment and overall, as well as by severity and relationship to study drug. Serious AEs and AEs leading to discontinuation of study drug will also be presented in the data listings and summarized by treatment and overall.

Actual values and changes from baseline for clinical laboratory test results, vital sign measurements, and 12-lead ECG results will be summarized by treatment at each time point using descriptive statistics (number of subjects, mean, SD, minimum, median, and maximum). Shift tables will be generated for clinical laboratory test results. Physical examination findings will be presented in a data listing.

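### SAP 9.1 attributes each AE by its onset alone, so an ongoing AE that worsens after a later dose is missing from the later treatment's column

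*Combined protocol and SAP*

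**What the plan says.** SAP 9.1 gives the attribution rule: "AEs will be summarized according to the most recent treatment received prior to the AE onset". Its example is an AE that occurs after the Period 1 dose "but before the administration of study drug on Day 1 of Period 2 will be summarized for study drug administered in Period 1". The same section bases percentages on the safety population and adds a counting rule: "A subject with 2 or more events within the same level of summarization will be counted only once in that level", using the most severe or most related incident. SAP 9.1 neither uses nor defines the term treatment-emergent, and it does not say what happens when an ongoing AE worsens after a later dose.

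The protocol is wider. Section 6.2.1.1 includes among treatment-emergent AEs "any event already present that worsens in intensity or frequency after exposure to the study drug". Section 7.3.2 plans that "Treatment-emergent AEs will be summarized by treatment and overall, as well as by severity and relationship to study drug". On recording, section 6.2.1.5 says "Changes in the severity of an AE should be documented to allow an assessment of the duration of the event" at each level of intensity, and adds: "An AE characterized as intermittent requires documentation of the onset and duration of each episode".

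All four sequences start with TPOXX alone (Treatment A) and give the four binder combinations (B to E) in Periods 2 to 5, with 7 days between doses.

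**The concern.** In a five-period crossover the by-treatment AE table is meant to show what followed each treatment. Under an onset-only rule, an AE that begins mildly after one dose and becomes severe after the next leaves no trace in the column of the treatment after which it became severe. The protocol's definition would count it there.

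The secondary objective is the safety and tolerability of TPOXX given with the binders. The fixed position of TPOXX alone makes the omission asymmetric: that column can retain a worsening that followed a binder, while no binder column can retain one that followed TPOXX alone.

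**Working it through.** The documents state no figure on this point, so there is none to reproduce. The check follows one AE through the rules and then counts the sequences.

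**1. One AE under the rules.** Take a continuous AE, Grade 1 after the Period 1 dose (TPOXX alone), still present at the Period 2 dose, and Grade 3 after it.

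- Protocol 6.2.1.1 read by treatment, as 7.3.2 requires: treatment-emergent under TPOXX alone at Grade 1, and under the Period 2 binder at Grade 3.
- SAP 9.1: one onset, in Period 1, so TPOXX alone only.

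The grade shown depends on how the change is recorded. Protocol 6.2.1.5 asks that it be documented but does not call for a new record with a new onset.

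| Recording | TPOXX alone | Period 2 binder |
|---|---|---|
| One record, worst grade | Grade 3 | nothing |
| One record, grade at onset | Grade 1 | nothing |
| New record at the grade change | Grade 1 | Grade 3 |

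Only the third row matches the protocol, and neither document specifies it.

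**2. Which column keeps the event.** Inputs: sequences ABCDE, ACEBD, ADBEC and AEDCB, 1:1:1:1 (protocol 5.3). Assumptions: equal numbers per sequence, no dropout, equal onset rates, and the same chance of persisting and worsening at every crossing.

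- Worsening at the next dose (adjacent crossings): 4 sequences × 4 = 16. A is the earlier treatment in 4 (25%) and the later in 0. Each binder is earlier in 3 (18.75%) and later in 4. The binders together are earlier in 12 (75%).
- Worsening at any later dose (all pairs): 4 × 10 = 40. A is earlier in 16 (40%) and later in 0. Each binder is earlier in 6 (15%) and later in 10. The binders together are earlier in 24 (60%).

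Binder-to-binder shifts cancel when the four binder combinations are pooled. Shifts from A to a binder do not. Pooling is used here only to show net direction; SAP section 4 lists the treatments separately.

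**3. Unequal onset rates.** The documents give no AE rates. Let the onset rate under A be r times that under each binder.

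- Adjacent crossings: A share = 4r/(4r + 12) = r/(r + 3). It is 14% at r = 0.5, 25% at r = 1 and 57% at r = 4. It exceeds 50% only if r > 3. A stops being the largest single source if r < 0.75, where 4r < 3.
- All pairs: A share = 16r/(16r + 24) = 4r/(4r + 6). It is 25% at r = 0.5, 40% at r = 1 and 73% at r = 4. It exceeds 50% only if r > 1.5.

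**4. Size of one event.** Assume that all 44 planned subjects are dosed and form the safety population. One subject is then 1/44 = 2.3 percentage points.

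- Incidence: the later treatment's column is 2.3 points too low. The earlier column is right, because the AE did begin there.
- One severity row, with one record at worst grade: the earlier column is up to 2.3 points too high and the later column 2.3 points too low, so their difference moves by up to 2/44 = 4.5 points.

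**The case against.** The strongest case is that this is a small gap in wording. Protocol 6.2.1.1 defines treatment-emergence relative to exposure to study drug, not dose by dose. Section 7.3.2 says by treatment but gives no attribution rule, and SAP 9.1 supplies one with an example. An AE must still be ongoing when the next dose is given and must then worsen. The AE tables are descriptive, no decision rests on them, and every AE is also listed. Most of this stands and limits the size. It does not remove the conflict: once 7.3.2 promises treatment-emergent AEs by treatment, the worsening part of the definition needs a place in each column, and listings do not replace that summary.

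The documents do not support four stronger inferences that a reader might draw:

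- *Recurrences are lost too.* Protocol 1.4.1 notes that "Headache and nausea have been the most common adverse events (AEs) in clinical studies completed to date", and such events could be intermittent. But 6.2.1.5 requires an onset for each episode, and an episode that starts after a binder dose can be placed under that binder by the SAP's own rule. SAP 9.1 refers to AE onset, not to the first onset. At most it is unclear whether several episodes form one AE for analysis.
- *Most affected events sit under TPOXX alone.* With equal onset rates, 60% to 75% would have started under a binder.
- *The counting rule moves the worst grade to the earlier treatment.* That sentence chooses between two or more events at one level of summarization. It does not govern grades within one AE.
- *The size should be worked at 36 subjects.* That is the target for evaluable subjects; SAP 9.1 uses the safety population.

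**Conclusion.** The point holds for worsening. Followed as written, and unless the site opens a new AE record at each grade change, SAP 9.1 leaves an ongoing AE that worsens after a later dose out of that treatment's column. If the record carries the worst grade, that grade appears under the earlier treatment.

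The net direction is fixed by the design. TPOXX alone never follows a binder, so this mechanism can only overstate its severity and understate that of the pooled binder combinations. The incidence of TPOXX alone is not inflated.

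Each event moves a column by 2.3 points if 44 subjects are dosed. The number of such events cannot be derived, because no rate of AEs ongoing at the next dose is given; with doses 7 days apart it is probably small. The correction is worth making because a stated rule gives a wrong table entry and the remedy is cheap.

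**What to change.** In SAP 9.1, define treatment-emergent AEs by treatment and add two rules:

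- An AE whose grade rises on or after a dose and before the next dose also counts as treatment-emergent under that treatment, at the highest grade reached in that interval. The earlier part stays under the earlier treatment at its own grade.
- Each documented episode of an intermittent AE is attributed by its own onset.

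Both rules draw on the severity-change and episode data that protocol 6.2.1.5 already requires. Before programming, confirm that the eCRF dates each grade change closely enough to place it before or after a dose.

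The cost is SAP wording and some programming. One AE may then count under more than one treatment, so a table footnote should say that the treatment columns need not add up to the overall column.
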